6.6.5. Vital Signs

Systolic and diastolic blood pressure (mmHg), height (cm), and weight (kg) at baseline and at all subsequent scheduled time points will be summarized. Changes from baseline value will be presented for all scheduled time points.

All recorded vital sign data will be listed.

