Brief physical examination	Measure vital signs (temperature, blood pressure, and heart rate), weight, and ECOG performance status (Table 13). Perform symptom-directed examination and investigate any new abnormalities.
Adverse events review	Record any new or ongoing adverse events.
Concomitant medications review	Record any new medications or changes in ongoing medications.
Study drug accountability	Record study drug returned and remind patient to return all bottles (used and unused) at each future visit.
Local Laboratory Evaluations	
Serum chemistry, hematology	Refer to analytes listed in Table 12 .

5.2.4 Week 13

The visit window is ± 3 days. Drug supply must be taken into account if a window is used to schedule the next visit.

Week 13 procedures are listed in [Table 4](#).

Table 4: Week 13 Procedures

Activity / Assessment	Comment
General Activities	
Brief physical examination	Measure vital signs (temperature, blood pressure, and heart rate), weight, and ECOG performance status (Table 13). Perform symptom-directed examination and investigate any new abnormalities.
Adverse events review	Record any new or ongoing adverse events.
Concomitant medications review	Record any new medications or changes in ongoing medications.
Enzalutamide dispensing (if applicable)	As appropriate according to PSA value. Per PSA assessment below, patients with PSA values increased from baseline may discontinue study drug and have safety follow-up unless the investigator considers continuation of study drug to be beneficial. Provide the patient with an 8-week supply. Provide instructions for dosing, storage, and return of all bottles (used and unused) of study drug at future visits.
Study drug accountability	Record study drug returned and remind patient to return all bottles (used and unused) at each future visit.
Local Laboratory Evaluations	
Serum chemistry, hematology	Refer to analytes listed in Table 12.
PSA	Patients with PSA values increased from baseline may discontinue study drug and have safety follow-up unless the investigator considers continuation of study drug to be beneficial.
Imaging Evaluations	
	Refer to imaging instruction manual for imaging acquisition requirements.
¹⁸ F-NaF PET/CT imaging (NaF-2)	

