8.5 Physical Examinations, Vital Signs, and Electrocardiograms

The investigator will perform complete or brief physical examinations according to the schedule of activities ([Appendix 2](#)).

Complete physical examinations will be per standard care at the study site and may include dermatologic, cardiac, respiratory, lymphatic, gastrointestinal, musculoskeletal, and neurologic systems, and other systems if clinically indicated by symptoms. Weight will be measured as part of the examination. Height will be measured only at screening.

Brief physical examinations will be directed toward patient-reported symptoms and include investigating any new abnormalities. Weight will be measured as part of the examination.

Vital sign measurements will include temperature, blood pressure, and heart rate.

Standard 12-lead ECGs will be obtained and read locally for study eligibility purposes.

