10.4 Safety Analyses

All safety analyses will be performed using the safety population.

Safety analyses will be summarized. Safety will be evaluated by the incidence of serious adverse events, incidence and severity of adverse events, incidence of permanent treatment discontinuation due to adverse events, and incidence of new clinically significant changes in clinical laboratory values and vital signs.

The treatment-emergent period is defined as the duration of time from the date and time of the first dose of study drug treatment (enzalutamide) through 30 days after the last dose of study drug treatment (permanent treatment discontinuation) or the day before initiation of cytotoxic chemotherapy, a lutamide (bicalutamide, nilutamide, or flutamide), or a new investigational therapy, whichever occurs first.

Adverse events will be coded according to the Medical Dictionary for Regulatory Activities (MedDRA) and tabulated by system organ class and by preferred term within each system organ class. Tabular summaries will include the incidence overall (number and percentage of patients with treatment-emergent adverse events classified by system organ class and preferred term); incidence by intensity (severity graded according to the CTCAE, version 4), causality, seriousness, and outcome (eg, leading to discontinuation of study drug); and other presentations as appropriate.

Serious adverse events occurring before study treatment will be tabulated separately if considered related to study procedure.

Patients with the same adverse event reported more than once will be counted once at the maximum severity or strongest relationship to study drug.

Toxicity for laboratory parameters (hematology, serum chemistry) will be graded using the CTCAE, version 4 when applicable. Shift tables will be provided as appropriate for each parameter to summarize baseline toxicity grade versus postbaseline toxicity grade. For each laboratory parameter that is not gradable by the CTCAE, a shift table based on the normal range (low, normal, and high) will be provided to summarize baseline result versus postbaseline result. For each laboratory parameter, the baseline laboratory value is defined as the last laboratory value collected on or before the date of the first dose of study drug.

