- [6] At investigator discretion (eg, significant bone pain or a skeletal-related event for ^{99m}Tc-MDP bone scintigraphy; or suspicion of soft tissue disease progression for CT or MRI) or (for ^{99m}Tc-MDP bone scintigraphy only) to coincide with NaF-3 unless bone disease progression was confirmed earlier. Progression at week 13 or earlier will require a confirmatory ^{99m}Tc-MDP bone scintigraphy at least 6 weeks later showing at least 2 additional new lesions related to prostate cancer (compared with the previous scan). After week 13, no confirmation of progression will be required if at least 2 new lesions related to prostate cancer are observed. If no bone disease progression was seen by ^{99m}Tc-MDP bone scintigraphy before NaF-3, then ^{99m}Tc-MDP bone scintigraphy will be required at the time of NaF-3. Send copies of bone scintigraphy images to the central imaging vendor for archiving.
- [7] Includes vital signs (temperature, blood pressure, heart rate), ECOG performance status, weight. Height at screening only.
- [8] May skip if performed within prior 3 days.
- [9] Symptom-directed and includes vital signs, ECOG performance status, and weight.
- [10] Repeats every 16 weeks ±7 days after week 21.
- [11] Collect serious adverse event information from the time of signed informed consent and nonserious adverse event information from the time of first dose of study drug through 30 days after the last dose or initiation of cytotoxic chemotherapy, a lutamide (bicalutamide, nilutamide, or flutamide), or a new investigational therapy, whichever occurs first. Phone patients for follow-up if they do not come to the clinic.
- [12] Complete, sign, and fax or email the form with requested items to the medical monitor or designee at least 2 business days before the anticipated day 1 visit, if possible. Patient may proceed to day 1 visit when medical monitor or designee approves by signed form or email correspondence.
- [13] Patients with PSA values increased from baseline may discontinue study drug and have safety follow-up unless the investigator considers continuation of study drug to be beneficial.
- [14] Refer to laboratory and imaging instruction manuals for sample processing and imaging acquisition requirements. Interpretation of ¹⁸F-NaF PET/CT imaging performed at the central imaging vendor.
- [15] Collect predose.
- [16] At time of NaF-3.

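### SAP 6.6.5 tracks height, which is measured only at screening, leaves heart rate and temperature to a listing, and gives the protocol's vital-sign incidence measure no output of its own

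*SAP*

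**What the plan says.** SAP 6.6.5 names the variables: "Systolic and diastolic blood pressure (mmHg), height (cm), and weight (kg) at baseline and at all subsequent scheduled time points will be summarized". It adds: "Changes from baseline value will be presented for all scheduled time points". Everything else goes to a listing: "All recorded vital sign data will be listed".

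Protocol 8.5 defines the term differently: "Vital sign measurements will include temperature, blood pressure, and heart rate". On height it says: "Height will be measured only at screening". Footnote 7 of the schedule of activities (Protocol Appendix 2) repeats this: "Height at screening only". The instruction for on-treatment examinations, for example at week 5 (Protocol Table 3), is "Measure vital signs (temperature, blood pressure, and heart rate), weight, and ECOG performance status (Table 13"; height is not in it.

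Protocol 10.4 and the synopsis list the safety measures. One of them, separate from the incidence of adverse events, is "incidence of new clinically significant changes in clinical laboratory values and vital signs".

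**The concern.** The SAP section does not match the data the protocol collects. It asks for repeated summaries of a variable with no repeat measurement, and omits two variables measured at every examination. Nothing in the SAP explains the choice. Where the SAP departs from the protocol on purpose, as when it replaces the intent-to-treat population with the As Treated population (SAP 4), it says so and gives a reason.

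The second issue is the named incidence measure. By-visit summaries describe a distribution at each visit. They do not count patients whose value became abnormal after starting treatment. Protocol 1.2 lists hypertension among the common adverse reactions in the phase 3 post-docetaxel study, so a count of patients with newly abnormal blood pressure is of direct interest. At stake is the completeness of the descriptive safety report, not any efficacy conclusion.

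**Working it through.** No plan figure needs reproducing, so the check compares the texts.

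**Step 1. Variables collected against variables summarised.** Collection is taken from Protocol 8.5, Tables 2 to 5 and 8, and Appendix 2. Examinations fall at screening, day 1, weeks 5, 13 and 21, every 16 weeks after that, and safety follow-up.

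| Variable | Protocol vital sign? | Measured after baseline? | By-visit and change summary in SAP 6.6.5? |
|---|---|---|---|
| Blood pressure | yes | yes | yes |
| Heart rate | yes | yes | no, listing only |
| Temperature | yes | yes | no, listing only |
| Weight | no | yes | yes |
| Height | no | no | yes |

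Of the 3 protocol vital signs, 1 is summarised and 3 − 1 = 2 are not. Of the 4 variables the SAP summarises (systolic pressure, diastolic pressure, height, weight), 1 has no scheduled post-baseline value. Its baseline value is already reported under SAP 6.5.1.

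**Step 2. The named incidence measure.** It has a laboratory half and a vital-sign half. For laboratory values, SAP 6.6.4 plans toxicity grading, baseline-to-worst shift tables and counts of liver-test elevations. For vital signs, SAP 6.6.5 gives no criterion, category, shift table or count. Dedicated vital-sign incidence outputs planned: 0.

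**Step 3. The indirect route.** Under Protocol 8.3.1 a vital-sign abnormality becomes an adverse event if it causes symptoms, needs intervention, leads to interruption or discontinuation, or is clinically significant in the investigator's judgement. SAP 3.5 then requires it to be new or worse on treatment, and SAP 6.6.1 tabulates it by preferred term. Some of the information therefore reaches a table. No SAP sentence says that these tables stand in for the vital-sign measure or names the terms to read.

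**Step 4. Where an extreme value would appear.** SAP 5.2.7 includes the minimum and maximum in its descriptive statistics. As an illustration, assume one patient in 20 has a systolic rise of 40 mm Hg and the others do not change. The mean moves by 40/20 = 2 mm Hg, but the maximum change is 40 mm Hg, so the value is visible. What the table does not give is a count of patients newly abnormal relative to baseline, where one patient would be 1/20 = 5%.

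**Step 5. Unscheduled visits.** SAP 5.2.4 brings unscheduled assessments into worst on-treatment safety derivations, but SAP 6.6.5 has no worst-value output and is limited to scheduled time points. As that section is worded, a reading at an unscheduled visit, which Protocol 5.2.7 allows for assessing toxicity, enters no vital-sign summary. The general inclusion of unplanned data (SAP 2) and the windows of SAP Appendix 3 might let one in when it lies closest to a target day, but not because it is the worst value.

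**The case against.** The strongest reply is that little is lost. All recorded vital signs are listed, and a listing for about 20 patients can be read in full. Investigator-judged significant abnormalities receive an incidence through the treatment-emergent adverse event tables, and the protocol gives no other definition of clinical significance for vital signs. Blood pressure, where the hypertension signal would appear, is the vital sign that is summarised. SAP 2 also reserves a general right to modify the protocol's plans.

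Much of this stands, and it rules out several stronger readings:

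- A reader might infer that summary means would hide a single outlier. They would not, because SAP 5.2.7 reports the maximum as well.
- A reader might infer that a whole planned table is empty. Only the post-baseline height cells are; blood pressure, weight and baseline height are reported.
- A reader might infer that the named measure has no result at all. It has an indirect one through adverse events.
- A reader might take the limits in exclusion criterion 17 as the natural definition of an on-treatment abnormality. They are eligibility limits, with nothing for temperature or for a high heart rate. With the systolic limit of > 170 mm Hg, a 40 mm Hg rise counts only from a baseline above 170 − 40 = 130 mm Hg; a change from 120 to 160 would be missed.

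The reply does not remove the mismatch. A listing is not an incidence, the protocol names the vital-sign measure separately from adverse events, and a general right to modify records no decision to drop it.

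**Conclusion.** The point holds as a minor inconsistency between SAP and protocol. The post-baseline height summaries cannot be produced, two of three protocol vital signs have no summary, and a separately named safety measure has no dedicated output and no stated substitute. The size is limited to descriptive safety reporting in a single-arm, estimation-only study of about 20 patients. The primary and secondary endpoints are unaffected.

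This rests on two readings: that SAP 6.6.5 is complete as published (no redaction mark falls in it), and that its restriction to scheduled time points means what it says. The 40 mm Hg case is illustrative and not a prediction.

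**What to change.** In SAP 6.6.5:

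1. Replace height with heart rate and temperature in the by-visit and change-from-baseline summaries. Height stays a baseline characteristic under SAP 6.5.1.
2. Add the number and percentage of patients with a new on-treatment vital-sign abnormality, meaning one absent at baseline. Base it on the worst on-treatment value, including unscheduled visits in line with SAP 5.2.4, and on reporting categories that the sponsor prespecifies. The figures in exclusion criterion 17 are one option, as reporting categories only and not as a clinical rule.
3. If the sponsor prefers no new table, state at minimum that the measure is reported through treatment-emergent adverse events, and name the vital-sign preferred terms that count.

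The cost is SAP wording and, under item 2, one small table. All the data are already collected.

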6.6.6. Electrocardiogram

Echocardiogram findings that were collected during the screening period will be listed by patient.

6.6.7. ECOG

[figure not shown]
Descriptive summaries at baseline and at the safety follow-up will be provided. These include:

• Number and percentage of patients for each of the six categories.

The ECOG performance status scores will be listed.

7. INTERIM ANALYSES

Not applicable.

9. APPENDICES

Appendix 1. Imputation of Missing/Partially Missing Dates

Missing data will not be imputed unless otherwise specified. Any imputations will occur at the analysis dataset level and not the raw dataset level. Additionally, in all patient data listings imputed values will be presented and flagged as imputed.

For safety analyses, incomplete date of last dose of study drug such as missing the day, the 15th of the month will be used to impute the missing data. When imputing partial last dose dates, the last assessment date and death date will be taken into consideration. This imputation rule will be used to determine the treatment-emergent period.

Adverse Events

[figure not shown]
The imputation rule for the safety analyses will be used to address the issues with partial dates. The imputed dates will be used to determine the treatment-emergent period. For adverse events with a partial date, available date parts (year, month, and day) of the partial date will be compared with the corresponding date components of the start date and end date of the treatment-emergent period to determine if the event is treatment emergent. When in doubt, the adverse event will be considered treatment emergent by default. The following rules will be applied to impute partial dates for adverse events:

If start date of an adverse event is partially missing, impute as follows:

- If both month and day are missing and year = year of treatment start date, then set to treatment start date.
- If both month and day are missing and year ≠ year of treatment start date, then set to January 01.
- If day is missing and(month and year) = (month and year) of treatment start date, then set to treatment start date.
- If day is missing and (month and year) ≠ (month and year) of treatment start date, then set to first of the month.
- If start date is completely missing, set to treatment start date as long as adverse event end date is not before treatment start date.

If end date of an adverse event is partially missing, impute as follows:

- If both month and day are missing, then set to December 31.
- If only day is missing, then set to last day of the month.
- If end date is completely missing, do not impute.

Concomitant Medications

When the start date or end date of a medication is partially missing, the date will be imputed to determine whether the medication is prior or concomitant (or both). The following rules will be applied to impute partial dates for medications:

If start date of a medication is partially missing, impute as follows:

- If both month and day are missing, then set to January 01.
- If only day is missing, then set to the first of the month.

If end date of a medication is partially missing, impute as follows:

[figure not shown]
- If both month and day are missing, then set to December 31.
- If only day is missing, then set to last day of the month.

If start date or end date of a medication is completely missing, do not impute.

Diagnosis of Primary Cancer

If the diagnosis date of primary cancer is partially missing, the following rules will be applied to impute partial dates:

- If both month and day are missing and year = year of treatment start date, then set to treatment start date.
- If both month and day are missing and year ≠ year of treatment start date, then set to December 31.
- If day is missing and (month and year) = (month and year) of treatment start date, then set to treatment start date.
- If day is missing and (month and year) ≠ (month and year) of treatment start date, then set to the last day of the month.

Appendix 2. Sample SAS Code

Sample SAS code follows below. The code is meant for a general start. Further dialogue between the programmer and statistician is encouraged.

KM quartiles and plot

```
proc lifetest data=x1 alpha=0.05 conftype=loglog plot=s;
time months*eventn(0);
run;
```

The variable "months" is a continuous variable representing months of exposure. The variable "eventn" is a binary variable (0=censor, 1=event).

Hazard ratio

```
proc phreg data=x1;
model months*eventn(0) = group / rl alpha=0.05;
run;
```

[figure not shown]
The variable "months" is a continuous variable representing months of exposure. The variable "eventn" is a binary variable (0=censor, 1=event). The variable "group" is a binary variable for median cutpoint (below/above the median change from baseline).

Clopper-Pearson Confidence Interval

```
proc sort data=y1 out=y2;
by descending response;
proc freq data=y2 order=data;
tables response / binomial(exact) alpha=0.05;
run;
```

The descending sort is included to ensure that the response modeled is 1 and not 0. The input dataset y1 has a one-record-per-patient format similar to:

| PATIENT | RESPONSE |
|---------|----------|
| 1001 | 0 |
| 1002 | 1 |
| 1003 | 0 |
| ••• | ••• |
| ••• | ••• |

[figure not shown]

ANCOVA Analysis

```
proc mixed data=z1;
class treat studysite;
model efchg = treat efbase studysite;
lsmeans treat / cl alpha=0.05 om;
run;
```

The variables "efchg" and "efbase" represent change from baseline and baseline values respectively. The OM option is used when the categorical term "studysite" is used in the model. If "studysite" is not included for convergence reasons, then the OM option can be removed.

While there is only one treatment arm in this study, the inclusion of the fixed effect for "treat" is needed in order to produce the desired least squares mean.

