3.4. Baseline Variables

The date of first dose (start date) of study treatment is the earliest date of non-zero dosing of the study drug. The date of last dose of study treatment is the latest date of non-zero dosing of the study drug.

No windowing will be applied when defining baseline. Any deviations from the protocol specified window will be documented as protocol deviations. For efficacy analyses and baseline characteristics associated with tumor assessments, the last assessment prior to the date and time of first study drug will serve as the baseline assessment.

For safety, the last assessment performed on or prior to date of the first dose of study treatment will serve as the baseline assessment. If there are no observations meeting these criteria, then baseline is considered missing.

Post-baseline value is defined as a measurement taken after the first administration of study drug. Change from baseline is defined as (post baseline value – baseline value). Percent change from baseline is defined as [(post baseline value – baseline value)/(baseline value)] multiplied by 100%. Both date and time of study drug administration and measurement will be considered when calculating baseline value. If time is not available, then date only will be used.

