5.1. Hypotheses and Decision Rules

The primary purpose of this study is to assess the NaF imaging as a method for evaluating treatment response in bone lesions at the time of progression. The sample size of 20 patients was chosen for practical clinical considerations.

Due to the exploratory nature of this study, there is no formal hypothesis. Instead, estimation will be the primary aim.

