5.2.2. Nominal Timepoints

Visit windows will apply per Appendix 3. Analysis Windows for Reporting.

Note that NaF-1 and NaF-2 are scheduled for baseline and week 13, respectively. NaF-3, however, is more fluid and can occur depending on different disease progressions or 2-years of therapy, per Section 3.1. If NaF-3 occurs before the scheduled NaF-2, then that scan will be NaF-3, and the pre-planned NaF-2 will not exist.

For endpoints only collected once post-baseline at NaF-3 (eg, circulating tumor cells), the NaF-3 slotted value will be the measurement closest to the NaF-3 scan.

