6. ANALYSES AND SUMMARIES

All efficacy analyses will be based on the AT population. Any confidence intervals presented will be 2-sided 95% CI. No adjustments to the confidence intervals are planned for any multiple testing. The start day for time to event analyses will begin at the date of first study drug.

Safety analyses (adverse events, laboratory tests, etc.) will be based on the AT population.

A grid-summary of the efficacy analyses can be found in Appendix 4. Summary of Efficacy Analyses.

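### The hazard-ratio code splits a change from baseline at the sample median; with about 20 patients a continuous covariate would keep information that the split discards

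*SAP*

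**What the plan says.** SAP Appendix 2 gives one Cox model, "model months*eventn(0) = group / rl alpha=0.05". Its single covariate, `group`, "is a binary variable for median cutpoint (below/above the median change from baseline". The time variable "is a continuous variable representing months of exposure", and SAP Section 6 sets the origin for all such analyses: "The start day for time to event analyses will begin at the date of first study drug".

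SAP Section 3.4 fixes when the covariate can be known: "Post-baseline value is defined as a measurement taken after the first administration of study drug". For the imaging measures, Section 5.2.2 adds "Note that NaF-1 and NaF-2 are scheduled for baseline and week 13, respectively", and for early progressors "If NaF-3 occurs before the scheduled NaF-2, then that scan will be NaF-3, and the pre-planned NaF-2 will not exist".

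On size, Section 5.1 says "The sample size of 20 patients was chosen for practical clinical considerations". The same section sets no formal hypothesis and makes estimation the aim. Appendix 2 presents its code as a starting point to be discussed between programmer and statistician.

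The visible text does not show which variable is split, at which scan, or for which event. The efficacy grid in Appendix 4 is redacted after the secondary endpoint, and the visible section numbers skip 3.3 and 6.3.

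**The concern.** A patient just above the median and one far above it enter the model as identical, while two patients on either side of the median and almost equal enter as opposites. If risk changes steadily with the size of the change, this widens the confidence interval for no gain. In a study of about 20 patients that aims to estimate, precision is the main thing the analysis has to offer.

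The cutpoint is also whatever the median of these patients turns out to be. A hazard ratio for high versus low on that scale cannot be carried to another cohort.

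A separate question is the clock. A change from baseline is known only after dosing, yet time runs from the first dose. Whether that matters depends on the scan and the event, which are redacted.

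**Working it through.** The plan states no power, event count or information figure for this analysis, so there is no figure to reproduce.

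**Inputs.** From the SAP: about 20 patients, a median split, a 95% CI, first dose as time origin, week 13 at target day 85. Assumed, because not visible: 10 to 20 events, the distribution of the change, and the size and form of its effect.

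**1. Information lost by the split.** For a small log-linear effect in a Cox model, the information retained is (E|X − median|)² / Var(X).
- Normal: 2/π = 0.637, a loss of 36.3%. Then 20 × 0.637 = 12.7 effective events.
- Uniform: 25%. Laplace: 50%. Exponential: 1 − (ln 2)² = 52%. t with 5 df: 46%. Lognormal: 48% (σ = 0.5) to 73% (σ = 1).
- True effect a step at the median: no loss.

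**2. Precision of the split analysis.** With equal groups the 95% CI is the hazard ratio times or divided by exp(1.96 × 2/√events).
- 20 events: exp(0.877) = 2.40.
- 10 events: exp(1.240) = 3.45.

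Under the normal case, a continuous term estimating the same contrast shortens the log-scale half-width by √0.637 = 0.798. The factors become exp(0.877 × 0.798) = 2.01 and exp(1.240 × 0.798) = 2.69.

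**3. Simulation.** 1,000 trials per setting, 20 patients all with events, normal covariate, log-linear effect, likelihood-ratio test at 5%:

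| log-HR per SD | Continuous | Median split |
|---|---|---|
| 0 | 0.064 | 0.055 |
| 0.4 | 0.33 | 0.22 |
| 0.6 | 0.60 | 0.41 |
| 0.8 | 0.81 | 0.60 |

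Power is not a criterion of this plan; the table only shows that the loss in step 1 carries over to samples of 20.

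**4. Clock, if the change is taken at NaF-2.** Day 85 is 84 days after day 1, and 84/30.4375 = 2.76 months. Cox estimation uses only the order of the event times, so adding the same interval to every patient changes nothing: one simulated data set gave a hazard ratio of 2.769 with and without the shift. With no true effect and only patients event-free at week 13 analysed, the geometric mean hazard ratio was 0.96 and rejection 5.8%. Survival curves for such patients do move right by 2.76 months.

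**5. Clock, if the change is taken at NaF-3.** The scan date now differs by patient. Null simulations (20 patients, mean 12 months to progression, NaF-3 at 24 months at the latest) gave:

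| Assumed drift of the change with time on drug | Progression as outcome: HR, rejection | Later event as outcome: HR, rejection |
|---|---|---|
| None | 1.03, 5% | 0.97, 5% |
| 0.5 SD per year | 0.58, 17% | 0.78, 8% |
| 1 SD per year | 0.32, 52% | 0.60, 13% |

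The drift is an assumption; the documents give no figure for it.

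**The case against.** The best defence is that most of this analysis cannot be seen. The redacted sections may name a continuous model, a landmark, or both. The split variable need not be an imaging measure, since circulating tumor cells are also taken at baseline and at NaF-3. The code is offered as a template, and the analysis is not the primary or secondary endpoint. All of that stands and limits the weight of the point. It does not remove it, because the median split is the written definition of the covariate in the only hazard-ratio model shown.

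A linear term also has a cost. In about 20 patients a few extreme values can drive it. SAP Section 5.2.9 replaces zeros by 0.0001 before taking logs, and ln(0.0001) = −9.2 could dominate the fit. This stands too, and calls for a check of influential points.

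A reader might infer more from the time origin: that counting from first dose builds guaranteed event-free time into the hazard ratio, or adds 84 days to the survival quartiles of each group. The documents support neither. A common lead time leaves the hazard ratio unchanged (step 4). The Kaplan-Meier code has no `strata` statement and no restriction to patients with NaF-2, so as written it describes the whole input data set from first dose, a usual origin in a single-arm trial. A reader might also infer that a NaF-3 change is being used to predict progression. The scan and the event are redacted, and without drift step 5 showed no bias.

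**Conclusion.** The point holds as one about dichotomisation. The 36% figure rests on an approximately normal change and a log-linear effect, and neither is documented. Section 5.2.9 itself allows for marked skew, and under the skewed shapes tried the loss from splitting an untransformed change was larger. It would be wrong to state a loss of over a third as fact: the range is 25% to 73% for the shapes tried, and zero for a step at the median. That the cutpoint cannot be reused does not depend on these assumptions.

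The time origin is a conditional note only. It becomes a matter of display if groups come from NaF-2, and possibly one of bias if they come from NaF-3. The visible text does not show which applies.

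The correction is worth making because it costs little, but it concerns an exploratory analysis and leaves the responder proportion and SUV(hetero) untouched.

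**What to change.** In Appendix 2, replace `group` in the Cox model with the continuous change, using the log-ratio of Section 5.2.9 where the measure is skewed. Report the hazard ratio per SD with its 95% CI, and give the SD so that others can convert the result. Refit without influential patients, including any whose zero was replaced by 0.0001. Keep the median split for Kaplan-Meier display or as a secondary summary.

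Add two conditional sentences, or a cross-reference if the redacted text already covers them:
- If groups are defined by NaF-2, Kaplan-Meier curves by group start at the NaF-2 date, among patients event-free then.
- A NaF-3 change is not used to predict the progression that triggered NaF-3.

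The cost is a line or two of code, a few sentences in the SAP, and matching edits wherever the redacted sections describe the split. The hazard ratio is then read per SD instead of high versus low, and the linear form needs the influence check above.
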